9.4.2 Withdrawal from Study

Reasons: Possible reasons for withdrawal from study include, but are not limited to, the following:

- Withdrawal of consent
- Significant subject noncompliance, defined as refusal or inability to adhere to the prescribed dosing and follow-up regimen
- Investigator determines that it is in the best interest of the subject to withdraw from the study protocol, due to reasons other than an AE

Assessments and Procedures: Subjects may withdraw from the study or be withdrawn at the request of the Investigator or Sponsor at any time. Subjects who wish to withdraw completely from this clinical study during the treatment period should be encouraged to undergo safety assessments at the time of withdrawal. Additionally, if a subject is withdrawn on Day 3 or Day 4, an attempt should be made to collect any remaining PK blood samples scheduled for that day. Subjects withdrawn from the study need not undergo TOC or FU assessments.

Clinical Outcome Assessment: Subjects who withdraw from the study and are not assessed as clinical failures should be assessed as indeterminate for all remaining scheduled clinical assessments.

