9.7 GUIDANCE TO INVESTIGATORS ON WHEN TO END STUDY DRUG THERAPY

The duration of study drug in this study is a fixed 7-day course in all three Treatment Arms; therefore, subjects who are improving clinically will receive no less or no more than 7 days of the study treatment regimen. At Day 7 (EOT), an assessment of clinical outcome will be performed by the Investigator. A subject will be determined as a clinical cure at EOT if the subject is alive and the infection is sufficiently resolved such that further antibacterial therapy is not needed ([Section 13.2.2](#)). Note that subjects with CABP may have some residual findings related to infection (i.e., cough) requiring non-antibiotic ancillary treatment (e.g., expectorant) at EOT and still meet criteria for clinical cure.

If additional antibacterial therapy is required for the index CABP (e.g., progressively worsening CABP between Day 1 and Day 7, or gradually improving CABP that requires additional antibacterial therapy beyond 7 days), study drug should be discontinued, the subject will be deemed a clinical failure on the day of study drug discontinuation, and open-label antibacterial therapy will be started at the discretion of the Investigator. Administration of blinded study drug will not be allowed beyond Day 7. In cases of premature discontinuation of study drug, subjects should not be discontinued from the study itself; subjects should remain in the study and undergo all scheduled assessments at EOT, TOC and FU ([Section 11.0](#)).

The Investigator may use culture and susceptibility results from the local microbiology laboratory to help guide therapy; however, decisions to continue or discontinue study drug should be based on clinical response rather than susceptibility results (as nafithromycin susceptibility testing is not available at the local site). If the index CABP is caused by a microorganism that is not susceptible to fluoroquinolones, macrolides, or ketolides in vitro, the decision to continue or discontinue study treatment should be based on the subject's clinical course and the Investigator's clinical judgment. These cases should be discussed with the Medical Monitor prior to prematurely discontinuing study drug, and the rationale for this decision should be recorded in the source documents.

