11.1 SCREENING VISIT

Screening visit procedures must be completed within 24 h prior to randomization, in order to determine study eligibility. Potential subjects who do not meet entrance criteria may, as appropriate, be rescreened and undergo repeat the baseline assessments within 72 h of initial screening for possible enrolment into the study.

Local or regional laboratory results will be used to determine subject eligibility for study enrolment. Any protocol-required eligibility laboratory or radiological evaluations already performed as part of the subject's regular medical care or site's standards of care within 24 h (laboratory) and 48 h (radiology) before randomization do not have to be repeated to determine subject eligibility. In addition, laboratory assessments ([Table 3-1](#)) must be sent to the central laboratory as part of baseline safety assessments. *If local or regional laboratory results are not confirmed by central laboratory results, the subject should not be automatically withdrawn from the study or study drug.* The subject should be assessed for safety and the Medical Monitor must be contacted to confirm subject eligibility to remain on study.

Written and signed informed consent must be obtained before any protocol assessment is performed.

Clinical Assessments:

- Verify inclusion and exclusion criteria
- Obtain a complete medical and surgical history, including all active conditions and all conditions diagnosed within the previous 5 years
- Record all prior medications that have been administered within 14 days prior to the date of signing the informed consent
- Record height and weight, and estimate creatinine clearance (CrCl) using the following Cockcroft-Gault formula (use actual body weight):

For serum creatinine in mg/dL:

$$\text{Males: CrCl} = \frac{(140 - \text{age in years}) \times \text{weight (kg)}}{72 \times \text{serum creatinine (mg/dL)}}$$

$$\text{Females: CrCl} = \frac{(140 - \text{age in years}) \times \text{weight (kg)}}{72 \times \text{serum creatinine (mg/dL)}} \times 0.85$$

If the serum creatinine value reported is in Système International d'Unités (SI) units (i.e., $\mu\text{mol/L}$), convert to conventional units (mg/dL) using the following formula:

$$\text{Conventional units (mg/dL)} = \frac{\text{SI units } (\mu\text{mol/L})}{88.4}$$

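### For study-drug stops that are neither safety nor efficacy related, Sections 9.4.2 and 9.7 disagree on whether follow-up continues

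*Combined protocol and SAP*

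**What the plan says.** Section 9.4.2 (Withdrawal from Study) opens its list with "Possible reasons for withdrawal from study include, but are not limited to, the following". Besides withdrawal of consent, the list contains "Significant subject noncompliance, defined as refusal or inability to adhere to the prescribed dosing and follow-up regimen" and "Investigator determines that it is in the best interest of the subject to withdraw from the study protocol, due to reasons other than an AE". The section adds that the Investigator or the Sponsor may have a subject withdrawn at any time. It states two consequences:

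- Follow-up: "Subjects withdrawn from the study need not undergo TOC or FU assessments".
- Outcome: withdrawn subjects "not assessed as clinical failures should be assessed as indeterminate for all remaining scheduled clinical assessments".

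Section 9.7 (guidance on ending study drug therapy) points the other way: "In cases of premature discontinuation of study drug, subjects should not be discontinued from the study itself". It continues that "subjects should remain in the study and undergo all scheduled assessments at EOT, TOC and FU".

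Section 9.4.1 deals with stopping study drug under two heads only:

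- Safety (9.4.1.1): study assessments go on at every visit, and the outcome may be cure or failure.
- Insufficient effect (9.4.1.2): EOT is done on the day of stopping, only safety assessments are asked for at TOC, FU is encouraged, and the outcome is failure.

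There is no head for any other reason.

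**The concern.** Ending study drug and ending observation are separate events, and Section 9.7 treats them so. Section 9.4.2 lets them be merged for subjects who have not withdrawn consent. A subject who refuses tablets for no safety or efficacy reason, or whom the Investigator takes off for another non-AE reason, has no place in Section 9.4.1. Section 9.4.2 is the only section that names such reasons, so a site may well apply it. Another site could apply Section 9.7 to the same case and follow the subject to Day 31.

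What is then collected depends on the site:

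- Clinical outcome at TOC in the ITT and micro-ITT populations.
- Hospitalization prior to FU, which Table 13.2.4-1 makes indeterminate when FU data are missing.
- TEAEs, which Section 14.1.1 defines through FU. Safety is a primary objective (Section 7.1).

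Section 9.5 rules out replacement. The blinded course also runs longer than the active nafithromycin course: active drug ends on Day 3 in Arm A and Day 5 in Arm B (Section 8.1). A subject in those arms who gives up tablets afterwards has had the whole active regimen and missed only placebo. Study withdrawal would discard an informative TOC outcome for the short courses under study.

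**Working it through.** **1. Which rule applies to which stop**

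- Stop for safety: 9.4.1.1 keeps all visits. Consistent with 9.7.
- Stop for insufficient effect: 9.4.1.2 assigns failure, so the clinical outcome is not lost. Its visit wording (safety assessments only at TOC, FU encouraged) is weaker than 9.7, which asks for all scheduled assessments.
- Stop for any other reason, consent not withdrawn: no rule in 9.4.1. Under 9.4.2, TOC and FU may be skipped and the outcome is indeterminate; under 9.7, EOT, TOC and FU are done. This is the gap.
- EOT at withdrawal: Table 3-1, footnote c, asks for it on any premature withdrawal from study or study drug. Section 9.4.2 only encourages safety assessments and sets the remaining clinical assessments to indeterminate.

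**2. The plan's own precision figure**

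Inputs: 78% response and n = 75 per arm (Section 16.2.1); Clopper-Pearson method (Section 16.2.3.1). With x = 0.78 × 75 = 58.5, the interval is 66.94% to 86.75%, against the stated 66.9% to 86.7%. It reproduces. Section 16.2.1 gives no dropout rate, and the present point reveals no sample-size error.

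**3. Size per subject**

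ITT is all randomized subjects (Section 16.1.2), so k withdrawn subjects leave k/75 of an arm's TOC outcome unobserved:

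- k = 1: 1/75 = 1.3 points
- k = 2: 2/75 = 2.7 points
- k = 6: 6/75 = 8.0 points

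The values of k are assumptions; the documents give no count.

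**4. Illustration for the Day 4 endpoint**

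Assume a fraction w of an arm is withdrawn before the Day 4 assessment, would have responded at 78%, and stays in the denominator as indeterminate. Observed rate = 0.78 × (1 − w):

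- w = 2%: 76.4% (95% CI 65.2% to 85.5%)
- w = 5%: 74.1% (62.7% to 83.5%)
- w = 10%: 70.2% (58.5% to 80.2%)

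Withdrawal after that assessment leaves the primary endpoint unchanged. The same arithmetic would apply to ITT cure at TOC if 78% were assumed there.

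**5. Safety window**

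A subject withdrawn on Day 3 could miss up to 31 − 3 = 28 days of planned observation. This is an upper limit.

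**The case against.** Much can be said for the plan.

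- A reader might infer that failing to take doses forces a subject out of the study. The text does not say so. It joins dosing and follow-up, and can be read as needing failure of both. The reasons are only possible ones, and visits need not occur rather than must not. Section 9.4.2 permits loss of follow-up; it does not impose it.
- A reader might infer that everyone who merely stops study drug becomes indeterminate, so that failures are hidden. Sections 9.4.1.1 and 9.4.1.2 keep in the study those who stop for safety or insufficient effect. Section 9.7 makes a failure of anyone needing further antibacterial therapy for the index infection, and existing failures are exempt from indeterminate. In ITT an indeterminate subject is already not counted as a cure, so what is lost may as easily be a cure.
- A reader might blame this gap for losses from CE and ME. Section 16.1.4 separately requires 80% of intended doses. A subject who stops the blinded seven-day course after Day 3 has at most 3/7 = 43% and fails regardless of follow-up.
- A reader might take Section 11.1 as another exit, since after a central-laboratory disagreement "the Medical Monitor must be contacted to confirm subject eligibility to remain on study". The sentence before it says such a subject should not automatically be withdrawn from the study or study drug. What remains is silence on follow-up if the answer is no.
- The safety loss is softened by the EOT visit in Table 3-1 and by Section 14.1.5, which requires follow-up of known AEs and reporting of deaths within 30 days of last contact.
- The Section 9.7 sentence is worded generally but sits in a paragraph on subjects needing additional antibacterial therapy, so its reach to noncompliance is uncertain.

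These points narrow the concern to one group and show that no rule compels the loss. They do not settle which section governs that group. The doubts over Section 9.7's reach and over the joined dosing and follow-up phrase are further reasons to clarify. Section 16.4 leaves missing-data handling to the SAP, but no analysis rule restores visits that were not made.

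**Conclusion.** The point holds for subjects who stop study drug for reasons other than safety or insufficient effect and who have not withdrawn consent to follow-up. For them the plan allows two different courses, and the choice decides whether ITT and micro-ITT outcome at TOC, hospitalization outcome and TEAEs to FU are collected.

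Each such subject is 1.3 percentage points of an arm of 75. The number affected is unknown, so any total rests on an assumed rate. The Day 4 primary endpoint is at risk only from withdrawals before the Day 4 assessment. No error in power or sample size follows, and Section 16.2 describes the study as exploratory. This is an avoidable source of missing data that is cheap to close, and worth correcting on that basis.

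**What to change.** Reconcile Section 9.4.2 with Section 9.7, and align the TOC and FU wording of Section 9.4.1.2 with both. State that:

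- unless the subject withdraws consent to follow-up, stopping study drug for any reason does not end follow-up;
- EOT, TOC and FU are still sought, by telephone if the subject will not attend. Section 11.10 now limits telephone FU to clinical successes without AEs or significant abnormalities, so this fallback has to be written in;
- outcome is assigned from observed data under Table 13.2.2-1, and indeterminate is used only when data are truly missing.

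Make no change to the reasons for, or timing of, stopping study drug. The cost is a short wording amendment, a letter to sites and a few more follow-up contacts, which Section 9.7 already expects.

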9.5 REPLACEMENT OF SUBJECTS

Randomized subjects who are withdrawn from the study will not be replaced.

9.6 STUDY TERMINATION BY SPONSOR AND TERMINATION CRITERIA

The Sponsor reserves the right to terminate an investigational site or this clinical study at any time. Reasons for termination may include, but are not limited to, the following:

- The incidence or severity of AEs in this or other studies of nafithromycin or moxifloxacin indicate a potential health hazard to subjects
- Serious or persistent noncompliance by the Investigators with the protocol, clinical research agreement, Form FDA 1572, or applicable regulatory guidelines in conducting the study
- Relevant ethics committee(s) or regulatory agency(ies) decision to terminate or suspend approval for the Investigator or clinical conduct at site

- Investigator request to withdraw from participation
- Subject enrolment is unsatisfactory

9.7 GUIDANCE TO INVESTIGATORS ON WHEN TO END STUDY DRUG THERAPY

The duration of study drug in this study is a fixed 7-day course in all three Treatment Arms; therefore, subjects who are improving clinically will receive no less or no more than 7 days of the study treatment regimen. At Day 7 (EOT), an assessment of clinical outcome will be performed by the Investigator. A subject will be determined as a clinical cure at EOT if the subject is alive and the infection is sufficiently resolved such that further antibacterial therapy is not needed ([Section 13.2.2](#)). Note that subjects with CABP may have some residual findings related to infection (i.e., cough) requiring non-antibiotic ancillary treatment (e.g., expectorant) at EOT and still meet criteria for clinical cure.

If additional antibacterial therapy is required for the index CABP (e.g., progressively worsening CABP between Day 1 and Day 7, or gradually improving CABP that requires additional antibacterial therapy beyond 7 days), study drug should be discontinued, the subject will be deemed a clinical failure on the day of study drug discontinuation, and open-label antibacterial therapy will be started at the discretion of the Investigator. Administration of blinded study drug will not be allowed beyond Day 7. In cases of premature discontinuation of study drug, subjects should not be discontinued from the study itself; subjects should remain in the study and undergo all scheduled assessments at EOT, TOC and FU ([Section 11.0](#)).

The Investigator may use culture and susceptibility results from the local microbiology laboratory to help guide therapy; however, decisions to continue or discontinue study drug should be based on clinical response rather than susceptibility results (as nafithromycin susceptibility testing is not available at the local site). If the index CABP is caused by a microorganism that is not susceptible to fluoroquinolones, macrolides, or ketolides in vitro, the decision to continue or discontinue study treatment should be based on the subject's clinical course and the Investigator's clinical judgment. These cases should be discussed with the Medical Monitor prior to prematurely discontinuing study drug, and the rationale for this decision should be recorded in the source documents.

10.0 TREATMENT OF SUBJECTS

Subjects will be randomized 1:1:1 to receive either oral nafithromycin tablets or oral moxifloxacin capsules (over-encapsulated tablets). The duration of therapy is 7 days (3 or 5 days of active oral nafithromycin followed by placebo to complete 7 days of therapy [Arms A and B, respectively] or 7 days of active oral moxifloxacin [Arm C]). Relevant matching placebo formulations (tablets and capsules) are used to maintain the blind.

10.1 STUDY DRUG

10.1.1 Oral Nafithromycin & Matching Placebo

Each subject randomized to receive nafithromycin (Arm A or Arm B) will receive oral nafithromycin administered as two 400 mg tablets — for a total of 800 mg — once daily.

Nafithromycin is a novel IV and oral antibacterial agent of ketolide class (molecular weight 859 Daltons), which is structurally related to macrolide class. The chemical nomenclature is: (11S, 21R)-3-Decladinosyl-11, 12-dideoxy-6-O-methyl-3-oxo-12, 11-{oxycarbonyl-[E-N-[1-(5-pyridin-2-yl)-1,3,4-thiadiazol-2-yl)-(S)-ethoxy]-carboxamidino]methylene}-erythromycin-A.

The nafithromycin and matching placebo tablets have been manufactured under GMP conditions and have undergone stability studies in compliance with regulatory norms. Oral nafithromycin 400 mg tablets and corresponding clinical placebo tablets are of white color, oval shaped, biconvex film coated, scored on both sides and debossed with W and 755 on either side of the score on one side (IB).

Storage and dispensing of nafithromycin tablets can be undertaken at room temperature (below 25°C) in its packaging (while protected from moisture). Detailed instructions regarding storage are presented in the Investigational Medicinal Product Dossier (IMPD).

The blinded products will be packaged in subject-specific blister wallets. Tablets are to be swallowed with water in an upright position.

10.1.2 Oral Moxifloxacin & Matching Placebo

Each subject randomized to receive moxifloxacin (Arm C) will receive oral moxifloxacin administered as a single 400 mg capsule (i.e., over-encapsulated tablet) once daily.

All other subjects, randomized to receive nafithromycin (Arms A and B), will receive moxifloxacin matching placebo.

The blinded products will be packaged in subject-specific blister wallets. Capsules are to be swallowed with water in an upright position.

Consult the summary of products characteristics or prescribing information ([Appendix V](#)) or other local dosing guidelines regarding preparation, storage, administration, maximum doses, contraindications, warnings, precautions, and AEs reported with the use of moxifloxacin.

10.2 TREATMENT COMPLIANCE

Treatment compliance will be documented in the eCRF by recording the date, time, and whether or not each oral dose of study drug was administered.

10.3 PRIOR AND CONCOMITANT MEDICATIONS

All prior systemic or inhaled antimicrobial agents (administered within 14 days prior to randomization) and all systemic or inhaled concomitant antimicrobial agents (administered during the study) will be documented.

A subject who received more than a single dose of any potentially-effective, short-acting, systemic antibacterial therapy for the current episode of CABP within 72 h before randomization will be excluded from the study ([Section 9.3](#)), unless there is unequivocal clinical evidence of treatment failure of the current episode of CABP (e.g., worsening signs and symptoms) after administration of an antibacterial agent other than a ketolide or fluoroquinolone.

Concomitant use of potentially effective systemic antibacterials or potentially effective inhaled antibacterials is not permitted.

Nafithromycin is a weak inhibitor of human cytochrome P450 (CYP) isoforms such as CYP3A4; specifically, nafithromycin is a 2-5x and 14-60x less potent inhibitor of CYP3A4 than telithromycin and solithromycin, respectively (details in IB). Nafithromycin is not an inhibitor of CYP2D6. In addition, nafithromycin does not induce enzyme activity or mRNA levels of CYP1A2, CYP2B6, or CYP3A4. Concomitant medications that induce P450 enzymes are contraindicated in this study. Specifically, prior (within 14 days prior to randomization) or concomitant use of cytochrome P450 liver enzyme inducers (e.g., phenobarbital, carbamazepine, griseofulvin, sulfonylureas, phenytoin, or rifampin) are excluded.

All other concomitant medications and nutrients necessary for the health and well-being of the subject are permitted.

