Nafithromycin attained a geometric mean $T_{1/2}$ of approximately 11 h in steady state at 800 mg/day in healthy human subjects (steady state was achieved on average within 3-4 days over the 600 to 1000 mg/d dose range). In addition, significant accumulation of nafithromycin in polymorphonuclear cells (PMNs) was observed.

Furthermore, superior tissue penetration observed in rodents — particularly in the target organ (lung) — is expected to drive superior pharmacodynamic (PD) activity, enabling a shorter duration of therapy of 3 to 5 days.

A multiple dose study was conducted to compare plasma, epithelial lining fluid (ELF) and alveolar macrophage (AM) concentrations of nafithromycin (800 mg administered once daily for 3 days) in healthy adult subjects. Each subject underwent one standardized bronchoscopy with bronchoalveolar lavage (BAL) at 3, 6, 9, 12, 24 or 48 h after the third oral dose of nafithromycin. Concentrations of nafithromycin were significantly higher in ELF and AM than simultaneous plasma concentrations throughout the 48 h period after 3 days of once-daily dosing. The ratios of ELF to plasma concentrations and of AM to plasma concentrations based the mean AUC_{0-24} values were 13.8 and 527, respectively.

Pharmacokinetic (PK) sampling:

Blood samples for PK analysis will be collected from all subjects on Day 3 and Day 4 at sites

	
where PK sampling is possible. Time points for PK sample collection will be:
 
 • Pre-dose: pre-dose PK sample will be collected within 10 minutes before dosing. • Post-dose at 2-4 h (Day 3) and 24-28 h (Day 4). Subjects who have been hospitalized are also required to have a post-dose PK sample at 6-10 h (Day 3).

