8.0 STUDY DESIGN

8.1 TYPE OF STUDY

This is a Phase II prospective, multicenter, multinational, randomized (1:1:1), double-blind, comparative study to determine the efficacy, safety, tolerability, and PK of oral nafithromycin versus oral moxifloxacin for treatment of adults with CABP. Study drug is defined as oral nafithromycin tablets or oral moxifloxacin capsules. Relevant matching placebo formulations (tablets and capsules) are used to maintain the blind.

Subjects providing informed consent and meeting all study eligibility criteria will be randomized into the study in a 1:1:1 ratio to either of the following 3 treatment arms:

- Arm A: Nafithromycin 800 mg (two 400 mg tablets) PO q24h for 3 days; subjects will receive matching placebo (two nafithromycin placebo tablets PO q24h) on Days 4 through Day 7, and one moxifloxacin placebo capsule PO q24h on Days 1 through 7, to maintain the blind
- Arm B: Nafithromycin 800 mg (two 400 mg tablets) PO q24h for 5 days; subjects will receive matching placebo (two nafithromycin placebo tablets PO q24h) on Day 6 and Day 7, and one moxifloxacin placebo capsule PO q24h on Days 1 through 7, to maintain the blind
- Arm C: Moxifloxacin 400 mg (one 400 mg over-encapsulated tablet) PO q24h for 7 days; subjects will also receive two nafithromycin placebo tablets PO q24h on Days 1 through Day 7, to maintain the blind

Baseline assessments for study eligibility will occur within 24 h prior to randomization using IXRS, stratified by region (US vs. ex-US) and PORT Risk Class (II vs. III/IV), will be used to assign subjects (1:1:1) to Arm A, Arm B or Arm C. Study Day 1 is defined as the day that the study drug is first administered, and subsequent study days are defined by the number of consecutive calendar days thereafter.

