 - The receipt of cancer chemotherapy, radiotherapy, or potent, non-corticosteroid immunosuppressant drugs (e.g., cyclosporine, azathioprine, tacrolimus, immune-modulating monoclonal antibody therapy) within the past 3 months, or the receipt of corticosteroids equivalent to or greater than 40 mg of prednisone per day for more than 14 days in the 30 days prior to randomization
7. Known or suspected primary or metastatic neoplastic lung disease, bronchiectasis, bronchial obstruction, chronic neurological disorder preventing clearance of pulmonary secretions, or severe COPD (severe COPD is defined as known [prior to Screening] FEV₁/FVC < 0.70 and FEV₁ $< 50\%$ normal); note that pulmonary function tests are not required at Screening
8. Compromised hepatic or renal function, including but not limited to: clinical evidence of end-stage liver disease (e.g., ascites, hepatic encephalopathy), screening serum total bilirubin > 2 times ULN (unless associated with an elevated indirect bilirubin typical of Gilbert syndrome), AST or ALT > 3 times ULN, serum creatinine > 2.0 mg/dl and/or BUN > 30 mg/dl. Other clinically-significant abnormal laboratory findings should be discussed with the Medical Monitor prior to the subject's entry.
9. History of *Clostridium difficile*-associated disease within 6 months prior to enrolment

10. History of hypersensitivity, known contraindication (e.g. lactose intolerance, lactase deficiency and glucose-galactose malabsorption etc.) or allergic reaction (e.g., anaphylaxis, urticaria, other significant reaction) to any ketolide, any fluoroquinolone antibiotic medicinal products or any of their excipients.
11. Current second- or third- degree atrioventricular block or sick sinus syndrome, uncontrolled atrial fibrillation, severe or unstable angina, congestive heart failure, myocardial infarction within 3 months of the Screening visit, clinically significant ECG abnormalities including QTcF > 450 msec (males) or > 470 msec (females), or requirement for medications known to cause QT prolongation
12. Prior (within 14 days prior to randomization) or concomitant use of cytochrome P450 liver enzyme inducers (e.g., phenobarbital, carbamazepine, griseofulvin, sulfonyleureas, phenytoin, or rifampin)
13. History of tendon rupture
14. Current peripheral neuropathy or myasthenia gravis
15. Known or suspected seizure disorder or other CNS disorders that may predispose the subject to seizures or lower the seizure threshold

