11.8 STUDY DAY 7 (END-OF-THERAPY [EOT])

Perform EOT assessments at any time during Day 7 after the final dose of study drug, or within 2 days following Day 7. Additional guidance on when to end study drug therapy is provided in [Section 9.7](#).

Administer study drug per the schedule in [Section 10.1](#).

Clinical Assessments:

- Record one set of vital signs, including body temperature (highest daily oral, rectal, or tympanic temperature), blood pressure, heart rate, respiratory rate, and pulse oximetry
- Perform a complete physical examination
- Assess CABP symptom severity ([Appendix III](#))
- Obtain a 12-lead ECG
- Identify, assess and record any AEs

- Record any concomitant medications
- Conduct clinical outcome assessment ([Section 13.2.2](#))

Central Laboratory Assessments:

- Obtain CBC, coagulation and chemistry panel ([Appendix IV](#))

Microbiological Assessments:

- If prior blood cultures are positive, repeated post-baseline blood cultures should be collected on the day that the positive blood culture is detected
- Repeated respiratory specimens should be obtained only if clinically indicated

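### The bar on QT-prolonging drugs applies at entry (Exclusion 11), but Section 10.3 does not carry it into the seven days of blinded treatment

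*Combined protocol and SAP*

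**What the plan says.** Exclusion 11 (Section 9.3, and the same in the Synopsis) lists cardiac conditions and QTcF limits of 450 msec for men and 470 msec for women, and ends with "or requirement for medications known to cause QT prolongation". Section 11.2 has all inclusion and exclusion criteria verified before randomization.

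The next criterion, Exclusion 12, is worded differently. It covers "Prior (within 14 days prior to randomization) or concomitant use of cytochrome P450 liver enzyme inducers", so it reaches into the treatment period by its own terms.

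Section 10.3 sets the rules for medication during the study. On antibacterials it says: "Concomitant use of potentially effective systemic antibacterials or potentially effective inhaled antibacterials is not permitted". It then contraindicates P450 inducers, repeating Exclusion 12. It closes with "All other concomitant medications and nutrients necessary for the health and well-being of the subject are permitted".

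Treatment is double-blind for 7 days in all arms (Section 8.1). Arm C takes active moxifloxacin throughout, while Arms A and B take active nafithromycin for 3 and 5 days respectively, then placebo.

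**The concern.** At entry the plan treats the need for a QT-prolonging drug as a reason not to randomize. Once a subject is on study drug, the section a site would consult before prescribing does not name the class, and its closing sentence permits necessary medication outside the two prohibited classes. The protection chosen at entry has no counterpart during exposure.

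What is at stake is subject safety. Someone prescribing for an intercurrent problem during the course will not ordinarily know the treatment assignment, and the subject may be taking moxifloxacin. No effect on the efficacy analysis is claimed.

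**Working it through.** The plan gives no figure for this point, and the finding rests on reading the provisions together.

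**Step 1. Compare the two neighbouring exclusions.**

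| Drug class | Exclusion criterion | Wording reaches concomitant use? | Restricted in Section 10.3? |
|---|---|---|---|
| P450 inducers | 12 | Yes, prior or concomitant | Yes |
| QT-prolonging drugs | 11 | Not expressly; refers to a requirement | No |

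The plan shows with the inducers how it extends an entry bar into treatment. It does neither thing for QT-prolonging drugs.

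**Step 2. Apply Section 10.3 to a new non-antibacterial QT-prolonging drug that is not a P450 inducer.** It is not a potentially effective antibacterial, so the first prohibition does not apply. It is not an inducer, so the second does not apply either. If it is needed for the subject's health, the closing sentence covers it. Within Section 10.3, nothing stops it.

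**Step 3. Look for the bar elsewhere.**

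- Section 10.1.2 sends sites to the moxifloxacin product information or other local dosing guidelines. Appendix V gives references to two product documents without their text. The pointer may discourage such use, but it states no prohibition, and the label content cannot be checked here.
- Section 9.4.1.1 lists examples of safety reasons for stopping study drug: an adverse event in the Investigator's judgment, Hy's law, and pregnancy or breastfeeding. The list is expressly not exhaustive. It names no QTc threshold and no trigger for starting a QT-prolonging drug.
- Section 8.1 provides daily Investigator assessment from Day 1 to Day 5. The visit procedures in Sections 11.2 to 11.8 record adverse events and concomitant medication on each dosing day. These would bring a new drug to notice but do not restrict it.
- Section 10.6 allows the code to be broken in a medical emergency when management requires it. Routine prescribing is not covered.
- Section 14.4 provides periodic blinded review by an internal committee. It cannot act when a drug is prescribed.

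**Step 4. ECG coverage.** Table 3-1 (footnote i) schedules on-treatment ECGs on Day 1, Day 3, Day 5 and EOT. Section 11.8 defines the last visit: "Perform EOT assessments at any time during Day 7 after the final dose of study drug, or within 2 days following Day 7". By visit day the gaps are:

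- Day 1 to Day 3: 3 − 1 = 2 days
- Day 3 to Day 5: 5 − 3 = 2 days
- Day 5 to EOT: 7 − 5 = 2 days, up to 9 − 5 = 4 days

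ECGs at these intervals may detect prolongation after the drugs have been combined. They do not prevent the combination, and the plan does not tie an unscheduled ECG to the start of such a drug.

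**Step 5. Can the number affected be estimated?** It would need a rate of new use and a QT effect. The documents give neither, so no count is offered.

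**The case against.** Several objections have force.

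- **The label may already forbid it.** Because of the blind, a site must treat every subject as possibly on moxifloxacin, so the pointer in Section 10.1.2 matters for all of them. A reader might infer that a site following the whole plan exactly is free to start a QT-prolonging drug. The documents do not support that, because it depends on label text that is not reproduced. What stands is narrower: Section 10.3 does not contain the restriction.
- **Exclusion 11 speaks of a requirement, not of current use.** Exclusion 5 uses similar language for treatment needed while the pneumonia is managed. Read that way, Exclusion 11 also keeps out subjects with a foreseeable need during the course. This is fair, and it confines the gap to a new, unforeseen need within 7 days.
- **The permission covers only necessary medication.** That is true, and it limits casual use. But Exclusion 11 is also about need, so the limit does not restore the bar.
- **The site can unblind.** A reader might infer that the site has no way to learn the assignment. Section 10.6 provides one in an emergency. The blinding concern therefore holds for ordinary prescribing only.
- **The size is unknown.** It is tempting to assume a starting rate and multiply by dosing days. Nothing in the documents supports a rate. Nor is every blinded day an active one: in Arm A "subjects will receive matching placebo (two nafithromycin placebo tablets PO q24h) on Days 4 through Day 7", and in Arm B "subjects will receive matching placebo (two nafithromycin placebo tablets PO q24h) on Day 6 and Day 7". No visible text attributes a QT effect to nafithromycin, and Sections 6.3 and 6.4.1 are largely redacted, so its dosing days cannot be counted as QT exposure.

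Finally, a reader might call this a contradiction between Sections 9.3 and 10.3. It is a gap: one section governs entry, the other treatment, and both can be followed.

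**Conclusion.** The point holds as an omission in Section 10.3 and is worth correcting as an inexpensive safety improvement. It is limited to new, unforeseen, non-antibacterial QT-prolonging drugs started during a 7-day blinded course, against a background of partial safeguards. Its size in subjects or in QT effect cannot be given. The conclusion rests on the visible text, in which no provision outside Section 10.3 restricts starting such a drug after randomization. It makes no assumption about what the moxifloxacin label says.

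**What to change.** In Section 10.3, add medications known to cause QT prolongation to those not permitted from first dose through EOT. Apply the rule identically in all three arms, so that it reveals nothing about assignment. Add that if such a drug becomes clinically necessary, the site contacts the Medical Monitor promptly, documents the decision to continue or stop study drug, and obtains an ECG as clinically indicated. Necessary care is then not withheld.

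The text change is one or two sentences. Sites must already recognize these drugs at screening for Exclusion 11, and the protocol already uses Medical Monitor contact elsewhere, for example in Section 11.1 and Appendix I.

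The running cost is occasional calls and possibly a few study-drug discontinuations. The CE population (Section 16.1.4) requires at least 80% of intended doses: 0.80 × 7 = 5.6, so 6 of 7 daily doses. A subject stopped after 5 doses has 5/7 = 71% and leaves that population. Under Section 9.4.1.1, a subject stopped for safety who still needs antibacterial treatment for the pneumonia is also assessed as a clinical failure. Both are reasons to leave the continue-or-stop decision to case-by-case judgment rather than make discontinuation automatic.
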